1.6.3 Preclinical Metabolism and Pharmacokinetics

RO7239361 exhibits PK properties consistent with Fc-fused proteins. Following intravenous (IV) administration, the steady-state volume of distribution (V_{ss}) of RO7239361 ranged from 0.034 to 0.069 in nonclinical species, suggesting RO7239361 largely resides in the extracellular

space. Total body clearance (CLTp) of RO7239361 was 0.68 mL/h/kg (mouse), 0.38 mL/h/kg (rat), and 0.21 mL/h/kg (monkey). The terminal half-life ($T_{1/2}$) was 65 (mouse), 117 (rat), and 129 hours (monkey). RO7239361 was slowly absorbed following SC administration with a T_{max} of 24 and 56 hours in the mouse and rat, respectively. RO7239361 demonstrated good SC bioavailability in mice and rats (approximately 84% in both species) and modest bioavailability in monkeys (~ 30%).

1.6.4 Clinical Pharmacology and Safety

The first-in-human, combined SAD and MAD study (CN001001) *has been completed*. Overall, 43 subjects received study drug/placebo during the SAD phase, and 97 subjects received study drug/placebo during the MAD phase. A single dose or multiple doses (up to 180 mg SC QW) of RO7239361 were generally safe and well tolerated.

There were no deaths, serious adverse events (SAEs) or AEs leading to discontinuation during the study.

The most frequently occurring AEs during the SAD phase were injection-site hemorrhage (n=3; 7.0%) and upper respiratory tract infection (n=3; 7.0%). The most frequently occurring AE during the MAD phase was injection-site erythema (n=12; 12.4%), followed by upper respiratory tract infection (n=11; 11.3%), and rash (n=9; 9.3%). All events were mild or moderate.

Injection-site and other skin reactions observed in the MAD phase were not associated with systemic symptoms, did not require cessation of study drug administration, and, in most cases, did not require treatment. ADAs to RO7239361 were detected in 45.2% and 27.8% of subjects receiving RO7239361 in the SAD phase and in the MAD phase, respectively. The presence of ADAs did not appear to affect exposure to RO7239361. Injection-site and other skin reactions were slightly more frequent in ADA-negative subjects (18.1%) than in ADA-positive subjects (6.9%).

No clinically significant dose-related changes in laboratory values occurred during the study. The most common marked laboratory abnormalities were transient elevations in CK and reductions in leukocytes. These laboratory abnormalities were not associated with AEs and were observed in both RO7239361- and placebo-treated subjects. There were no treatment-related changes in ECG parameters or vital sign measurements.

In Study WP40225, which was designed to compare the bioavailability of RO7239361 given at different injection sites, a total 76 healthy volunteers received single-dose SC injections of RO7239361 from a PFS in the abdomen, arm, and thigh.

There were no deaths, SAEs, or AEs leading to discontinuation during the study.

Overall, 25 of 76 subjects (32.9%) experienced AEs during the study. The incidence and severity of AEs were generally comparable across the groups with administration of RO7239361 in abdomen, arm, or thigh.

All AEs were mild or moderate in intensity. The most common AE was injection-site hemorrhage ($n=3$), followed by diarrhea, headache, and injection-site erythema ($n=2$ for each). All injection-site AEs were mild and resolved without treatment.

The most common marked laboratory abnormalities were transient reductions in leukocytes and elevation in ALT. These laboratory abnormalities were not associated with clinical symptoms and did not require pharmacological intervention. There were no treatment-related changes in ECG parameters or vital sign measurements during the study. Overall, 13 subjects had a positive ADA titer (≤ 2). The earliest detection of ADAs was on Day 64. The presence of ADAs did not appear to affect the exposure, safety, and tolerability of RO7239361.

Additional safety information on RO7239361 is available in the most recent version of the Investigator Brochure.

1.6.4.1 Pharmacokinetics of RO7239361

RO7239361 achieves peak concentrations *in serum* between 3 and 5 days post-injection and has a terminal half-life of approximately 7 to 10 days across all doses following single SC dose administration (5, 15, 45, 90, and 180 mg). The increase in exposure with dose of RO7239361 appeared to be generally proportional up to 90 mg but was greater than proportional at the highest dose of 180 mg (Study CN001001).

Following multiple RO7239361 administration, T_{max} of RO7239361 was achieved approximately 2–3 days after dosing. The half-life estimates following the last dose were from 10 to 13 days. PK parameters increased in a slightly greater than proportional manner over the explored dose range (15 mg Q1W to 180 mg Q1W) (Study CN001001).

In the current 226 study, the pharmacokinetics of RO7239361 in ambulatory boys with DMD were analyzed using a population-PK approach. The pharmacokinetics of RO7239361 were well characterized using a PD/PK model based on the target-mediated drug disposition concept, and body weight was found to be the only covariate. Steady state was reached after ~12 weeks of Q1W administration. The pharmacokinetics of RO7239361 appear to be dose proportional, considering the between-subject variability. T_{max} of RO7239361 was achieved within 24–30 hours after dosing.

1.7 Overall Risk–Benefit Assessment

More detailed information about the known and expected benefits and risks and reasonably anticipated AEs of RO7239361 are presented in the Investigator's Brochure.

The potential benefits of treatment with RO7239361 have not been established.

There are no identified risks to date related to RO7239361 administration. Potential risks include immunogenicity, hypersensitivity reactions, injection-site reactions, and adverse findings from nonclinical studies or observations with the use of other anti-myostatin agents. A more complete summary of potential risks is provided in the RO7239361 Investigator's Brochure.

Immunogenicity/Hypersensitivity: ADAs to RO7239361 were detected in subjects receiving RO7239361 in SAD and MAD phases of Study CN001001. Most subjects with injection-site or other skin reactions were ADA-titer negative, suggesting a lack of relationship between the presence of ADAs and risk for cutaneous AEs. In Study WP40225, 17.1% of the healthy subjects who received a SC single dose of RO7239361 in the abdomen, arm, or thigh had a positive ADA titer (low, ≤ 2). The presence of ADAs appeared to have no effect on exposure in both studies, and no subject developed an acute hypersensitivity reaction.

Subject safety will be closely monitored in this study. All subjects who are administered study drug will be closely monitored for possible immunogenicity-related AEs. If present, antibodies will be assessed for neutralizing activity by assessment of serum free myostatin levels and muscle volume endpoints. Subjects who do not enter a separate rollover treatment study of RO7239361 will enter the follow-up phase of the study. Subjects will be requested to provide immunogenicity samples at each visit during the 24-week follow-up phase ([Table 5.1-5](#)).

Potential Acute Hypersensitivity Reactions to RO7239361: No participants in Study CN001001 or WP40225 receiving RO7239361 developed an acute hypersensitivity reaction. The risk of a subject developing an acute hypersensitivity reaction to RO7239361 is considered low. However investigators and sites should be prepared to manage possible acute hypersensitivity reactions to initial doses of RO7239361. Management of acute hypersensitivity reactions is further described in Section [3.4.2.2](#).

Injection-Site Reactions may occur when a drug is injected subcutaneously. In the MAD phase of CN001001, mild injection-site erythema was the most common AE observed, occurring in 12.4% of subjects treated with RO7239361. AEs of injection-site erythema did not require treatment or cessation of study drug and were not accompanied by systemic symptoms. Injection sites will be rotated and inspected regularly. Injection sites will be monitored from Day 1 through the end of the study.

Teratogenicity (Fetal Malformation of Protruding Tongue): The presence of the fetal malformation of protruding tongue was noted in both pregnant rats and rabbits at all RO7239361 doses tested, which is considered a pharmacologically mediated effect of unknown consequence on postnatal development. Subjects who are sexually active should be advised to use appropriate methods of contraception (see Section [6.4](#)).

In addition, mortality and marked liver toxicity, including hepatocellular necrosis, were observed in pregnant rats (Section 1.4.2), which may reflect a species-specific effect and are not considered relevant to the use of RO7239361 in DMD patients since: 1) there was no mortality or evidence of liver toxicity at comparable or higher exposures in monkeys, juvenile male rats, and pregnant rabbits; and 2) there is no evidence for treatment-related clinical liver toxicity to date in humans given RO7239361. Liver function will continue to be closely monitored in studies of RO7239361 by following liver enzymes and bilirubin levels as well as clinical signs.

Liver Enzymes Elevation: Increased serum levels of AST and ALT observed in rats given RO7239361 for 6 months (see Section 1.4.2) were reversible with continued dosing and were not associated with histopathologic evidence of hepatocellular or skeletal muscle injury or inflammation. No ALT and AST elevations were observed at higher RO7239361 exposures in monkeys dosed for 6 months or juvenile rats dosed for 12 weeks. Monkey and juvenile rat exposures 17x and 10x, respectively, the lowest-observed-adverse-effect level (LOAEL) for the transaminase elevation in the 6-month rat study.

In the MAD phase of Study CN001001 in healthy subjects, 9 subjects (12.5%) receiving RO7239361 had ALT elevations $>1.25 \times$ upper limit of normal (ULN) (and $<3 \times$ ULN, except 1 subject with a single value of ALT elevation [4.6x ULN] on Day 99, with concurrent CK elevations). Most of the ALT elevations occurred only at single timepoint. None of the ALT elevations was accompanied with bilirubin elevations.

Taken together, the serum transaminase increases seen in rats in the 6-month study suggest a time-dependent finding that is likely rat specific. Regardless, potential hepatotoxicity will be assessed by monitoring of aminotransferases, bilirubin in serum, and evaluations of clinical signs and symptoms in subjects. The hepatocyte-specific markers gamma-glutamyl transferase (GGT) and glutamate dehydrogenase (GLDH) will continue to be used for liver monitoring.

Immunoglobulin G Suppression after Primary Immunization: A minimal to mild decrease in the IgG response to a primary immunization was observed in some animals treated with RO7239361. Given the small magnitude of the decrease in the IgG response to primary immunization and lack of effect of RO7239361 treatment on IgM response or IgG response to booster, potential effect of RO7239361 treatment on efficacy of immunization in humans is expected to be minimal. Caregivers should be advised to ensure that their child's immunizations are up to date prior to receiving study drug.

Potential Cardiac Effects of RO7239361: RO7239361 also recognizes GDF11, which has been implicated in heart failure associated with aging in mice²⁰. While the mechanism underlying the development of aging related re-modeling of the heart in mice likely differs from that underlying the development of heart failure in DMD, potential cardiac effects of RO7239361 will be monitored in this trial using electrocardiography and echocardiography. Notably, there have been no cardiac findings in animals who received RO7239361 in the toxicology studies. Further, no significant treatment-related changes in ECG parameters or vital signs have been observed in healthy adult subjects receiving single or multiple doses of RO7239361 in Study CN001001.

The most up to date safety information on RO7239361 is available in the most recent version of the Investigator's Brochure.

2 ETHICAL CONSIDERATIONS

2.1 Good Clinical Practice

This study will be conducted in accordance with Good Clinical Practice (GCP), as defined by the

International Conference on Harmonisation (ICH) and in accordance with the ethical principles underlying European Union Directive 2001/20/EC and the United States Code of Federal Regulations, Title 21, Part 50 (21CFR50).

The study will be conducted in compliance with the protocol. The protocol and any amendments and the subject informed consent will receive Institutional Review Board/Independent Ethics Committee (IRB/IEC) approval/favorable opinion prior to initiation of the study.

All potential serious breaches must be reported to Roche immediately. A serious breach is a breach of the conditions and principles of GCP in connection with the study or the protocol, which is likely to affect, to a significant degree, the safety or physical or mental integrity of the subjects of the study or the scientific value of the study.

Personnel involved in conducting this study will be qualified by education, training, and experience to perform their respective tasks.

This study will not use the services of study personnel where sanctions have been invoked or where there has been scientific misconduct or fraud (e.g., loss of medical licensure, debarment).

2.2 Institutional Review Board/Independent Ethics Committee

Before study initiation, the investigator must have written and dated approval/favorable opinion from the IRB/IEC for the protocol, Informed Consent Form or Assent Form, subject recruitment materials (e.g., advertisements), and any other written information to be provided to subjects. The investigator or Roche should also provide the IRB/IEC with a copy of the Investigator Brochure's or product labeling information to be provided to subjects and any updates.

The investigator or Roche should provide the IRB/IEC with reports, updates and other information (e.g., expedited safety reports, amendments, and administrative letters) according to regulatory requirements or institution procedures.

2.3 Informed Consent

Investigators must ensure that subjects are clearly and fully informed about the purpose, potential risks, and other critical issues regarding clinical studies in which they volunteer to participate.

For subjects unable to give their written consent, in accordance with local regulations, one or both parents, a guardian, or a legally acceptable representative (LAR) must be informed of the study procedures and must document permission by signing the informed consent form approved for the study prior to clinical study participation.

Each subject must be informed about the nature of the study to the extent compatible with his or her understanding. Should a subject become capable or reach the age of majority, his or her consent should be obtained as soon as possible. The explicit wish of a subject who is a minor or unable to give his or her written consent, but who is capable of forming an opinion and assessing information to refuse participation in, or to be withdrawn from, the clinical study at any time should be considered by the investigator.

Minors who are judged to be of an age of reason as determined by local requirements should also give their assent. The assent should be documented based on local requirements. Continued

assent should be documented when important new information becomes available that is relevant to the subject's assent.

Roche will provide the investigator with an appropriate (i.e., global or local) sample Informed Consent Form, which will include all elements required by ICH, GCP and applicable regulatory requirements. The sample informed consent form will adhere to the ethical principles that have their origin in the Declaration of Helsinki.

Investigators must:

- 1) Provide a copy of the consent form, assent form if applicable and written information about the study in the language in which the subject is most proficient prior to clinical study participation. The language must be non-technical and easily understood.
- 2) Allow time necessary for subject or subject's legally acceptable representative to inquire about the details of the study.
- 3) Obtain an informed consent signed and personally dated by the subject or the subject's legally acceptable representative and by the person who conducted the informed consent discussion.
- 4) Obtain the IRB/IEC's written approval/favorable opinion of the written informed consent form and any other information to be provided to the subjects, prior to the beginning of the study, and after any revisions are completed for new information.
- 5) If informed consent is initially given by a subject's legally acceptable representative or legal guardian, and the subject subsequently reaches majority, becomes emancipated, and/or capable of making and communicating his or her informed consent during the study, consent must additionally be obtained from the subject.
- 6) Revise the informed consent (and Assent Form if applicable) whenever important new information becomes available that is relevant to the subject's consent. The investigator, or a person designated by the investigator, should fully inform the subject or the subject's legally acceptable representative or legal guardian, of all pertinent aspects of the study and of any new information relevant to the subject's willingness to continue participation in the study. This communication should be documented.

The confidentiality of records that could identify subjects must be protected, respecting the privacy and confidentiality rules applicable to regulatory requirements, the subjects' signed ICF and, in the *United States*, the subjects' signed *Health Insurance Portability and Accountability Act* (HIPAA) authorization.

The consent form must also include a statement that Roche and regulatory authorities have direct access to subject records.

The rights, safety, and well-being of the study subjects are the most important considerations and should prevail over interests of science and society.

3 INVESTIGATIONAL PLAN

3.1 Study Design and Duration

This is a Phase Ib/II, multi-center, randomized, placebo-controlled, double-blind, multiple-ascending SC dose study to assess the safety and tolerability of RO7239361 in **Anti-Myostatin Adnectin (RO7239361)—F. Hoffmann-La Roche Ltd**
30/Protocol WN40226, Version 6

ambulatory boys with DMD. The study design schematic is presented in [Figure 3.1-1](#). Subjects will undergo screening evaluations to determine eligibility and baseline evaluations within 45 days prior to first administration of study drug/placebo. The initial 24-week double-blind phase will be followed by a 48-week OL phase and an OLE phase. The double-blind phase will have two parts: Part A and Part B.

Part A will include 3 dose panels of ≥ 5 to < 11 year old (the age of the subject is the age at randomization) ambulatory subjects with DMD and will consist of 4 weeks of double-blind dosing. Panels 1–3 will randomize approximately 8 subjects each (randomized 3:1 to RO7239361 or placebo). If, after all subjects in a panel have been randomized, and it is determined that older or younger ages are underrepresented, the panel may be opened to additional subjects of specific ages, even if 8 subjects have already been randomized. Opening Panels 1–3 to more than 8 subjects may provide more robust safety and tolerability data in certain age ranges. Roche will inform sites if and when dose panels are opened to additional subjects. All subjects will receive weekly (Day 1, Day 8, etc.) SC doses of RO7239361 or placebo.

Body Weight Tier	Fixed Dose (mg)/Volume (mL)
≥ 15 kg	4.0 mg/0.08 mL

Table 3.1-2: Panel 2 Dose

Body Weight Tier	Fixed Dose (mg)/Volume (mL)
≥ 15 kg to ≤ 45 kg	12.5 mg/0.25 mL
> 45 kg	20.0 mg / 0.4 mL

Table 3.1-3: Panel 3 Dose

Body Weight Tier	Fixed Dose (mg)/Volume (mL)
≥ 15 kg to ≤ 45 kg	35.0 mg/0.7 mL
> 45 kg	50.0 mg/1 mL

Table 3.1-4: Expansion Panel Dose

Body Weight Tier	Fixed Dose (mg)/Volume (mL)
≥ 15 kg to ≤ 45 kg	35.0 mg/0.7 mL
> 45 kg	50.0 mg/1 mL

The dose selected for the Expansion Panel will be a safe and well-tolerated dose that is less than or equal to the highest dose tested in the escalation panels. The Expansion Panel will provide additional safety, tolerability, *PD*, and functional data at a dose anticipated to be efficacious. As such, a dose that produces > 90% suppression in serum levels of free myostatin is expected to be efficacious. A review of safety data from Panels 1–3 supports the selection of the Panel 3 dose (35 mg for subjects ≥ 15 kg to ≤ 45 kg and 50 mg for subjects > 45 kg).

Part B will include 20 weeks of continued double-blind dosing in Panels 1–3 and an Expansion Panel of 24 weeks of double-blind dosing. The Expansion Panel will randomize approximately 16 subjects (randomized 3:1 to RO7239361 or placebo). The Expansion Panel will be initiated after at least 2 weeks of dosing has been completed by at least 6 subjects participating in Panel 3 and all available safety and tolerability data, including, but not limited to, injection-site reactions, reported AEs, clinical laboratory results, and vital sign *measurements* have been reviewed and deemed safe to proceed by the study investigators and the Roche Medical Monitor. The Expansion Panel may be opened to additional subjects to either explore another dose that may be safe and efficacious or randomize subjects of under-represented ages.

Upon completion of 24 weeks of double-blind dosing, all subjects will be eligible to enter the OL phase. In this phase, all subjects will receive open-label RO7239361 SC doses, weekly for 48 weeks. Subjects in the OL phase will receive the active dose corresponding to the dose in their originally assigned panel. Dosing in the OL phase may be adjusted based upon emerging safety and tolerability data and/or upon the results of the interim analyses (IAs) of the double-blind data. The schedule of events in the OL phase is described in [Table 5.1-3](#). Subjects who complete the 48-week OL phase, may continue in the OLE phase. Subjects in the OLE phase will continue to receive weekly doses of RO7239361 corresponding to the dose in their originally assigned panel for up to 228 weeks, or until RO7239361 is commercially available, whichever comes first. The study may be stopped earlier if the study is terminated by the Sponsor. In the OLE phase, all subjects will have visits every 12 weeks. The first visit in the OLE phase will occur 12 weeks after OL Week 48 and every 12 weeks thereafter for up to 228 weeks, or until RO7239361 is commercially available.

After approval of Version 6 of Protocol WN40226, and subjects have signed the corresponding updated Informed Consent Form, all participants will switch from the vial formulation to the PFS formulation of RO7239361. Subjects will continue to receive injections from a vial until the PFS becomes available at the site, based on availability of supplies and local approvals.

During the OLE phase, all subjects will switch from the vial formulation to PFS dosage formulation for weekly doses of study drug, corresponding to the same dose in Panel 3 (35 mg dose if a subject's body weight is ≥ 15 kg to ≤ 45 kg and the 50-mg dose if the subject's body weight is >45 kg). Subjects will receive their first dose of RO7239361 from a PFS during a scheduled clinic visit and will return to the clinic for the second PFS dose 1 week later. In addition, subjects will come to the clinic on Day 45 after the switch to the PFS (approximately 2 days after dosing at home) for PK blood sampling. Visits will take place every 12 weeks thereafter, as originally scheduled for the OLE phase.

[figure not shown]
Any subject who discontinues from the study early or who does not enroll in a rollover protocol should enter the follow-up phase of the study. The follow-up phase of the study is up to 24 weeks in length after the last dose.

Up to five IAs are planned until all subjects have completed Week 72 of the study, after which additional IAs may be conducted. The content and timing of the IAs are described in [Section 8.5](#).

Measures of function, including TFTs (4SC, 4SD, 10-m walk/run, standing from supine), 6MWD, the NSAA, PFTs, manual myometry measures of upper and lower extremity strength, ankle range of motion, and PUL measures of upper extremity motor ability, as well as safety assessments (e.g., ECG, echocardiogram, laboratory tests, and physical exams) and other exploratory assessments (e.g., DXA scan, serum and urine biomarkers) will be collected at selected timepoints as specified in [Table 5.1-1](#) through [Table 5.1-2](#).

Subjects may have ECGs, echocardiograms and laboratory assessments during the follow-up phase, as needed, to follow up on AEs. Subjects in the follow-up phase will be followed for up to 24 weeks after last dose for measurement of anti-RO7239361 antibodies (ADAs) and immunological AE assessment ([Table 5.1-5](#)).

Figure 3.1-1: Study Design Schematic

Subject safety will be closely monitored in this study.

Approximately 265 mL of blood will be drawn from each subject during the study.

The duration of the study is *up to approximately 6 years* (a 45-day [approximately 6-week] screening phase+24-week double-blind phase+48-week OL phase+228 weeks of OLE phase+24-week follow-up phase). The end of the study is the last visit in the follow-up phase in the study, up to 24 weeks after last injection.

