Upon completion of the 48-week OL phase, all subjects will have the option to continue treatment in the OLE phase. Dosing in the OLE phase may be adjusted based on emerging safety and tolerability data and/or upon the results of IAs. *During the OLE phase, all subjects will switch from the vial formulation to a prefilled syringe (PFS) dosage formulation corresponding to the same dose from Panel 3 (i.e., the 35-mg dose if a subject's body weight is ≥15 kg to ≤45 kg and the 50-mg dose if the subject's body weight is >45 kg).* The schedule of events in the OLE phase is described in Table 5.1-4.

[figure not shown]
Any subject who discontinues from the study early or who does not enroll in a rollover protocol should enter the follow-up phase of the study. The follow-up phase of the study is up to 24 weeks in length. Subjects should provide immunogenicity samples at all follow-up visits.

Up to five IAs are planned. The content and timing of the IAs are described in Section 8.5 of the protocol.

Measures of function, including TFTs (4SC, 4SD, 10-m walk/run, stand from supine), 6MWD, the NSAA, manual myometry measures of upper and lower extremity strength, ankle range of motion, PFTs, and PUL measures of upper extremity motor ability, echocardiograms, laboratory assessments, MRI and MRS scanning of the right thigh

will be collected during the double-blind phase, OL phase, and follow-up phase at the intervals specified in Table 5.1-2 to Table 5.1-4 (MRS procedures will be completed at selected sites, based on completed training). Study visits will occur as indicated in Table 5.1-1 through Table 5.1-4.

Figure 1: **Study Design**

Study Population:

Key Inclusion Criteria:

- Males, \geq 5 to < 11 years of age at time of randomization
- Diagnosis of Duchenne muscular dystrophy, confirmed by medical history (e.g., onset of clinical signs or symptoms before 6 years of age together with an elevated serum creatine kinase level) and by genotyping
- Subjects \geq 15 kg
- Ambulatory without assistance
- Subjects must be receiving corticosteroids (prednisone, prednisolone, or deflazacort) for at least 6 months prior to the start of study drug, with no significant change in dosage (> 0.2 mg/kg) or dosing regimen for at least 3 months prior to the start of study drug, with the expectation that dosage and dosing regimen will not change significantly for the duration of the study.
- 4SC \leq 8 seconds at screening (Day -45 to Day -7)

Key Exclusion Criteria:

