Subjects will receive SC doses of RO7239361/placebo weekly. During Part A (first four weeks of Panels 1–3), study drug should be administered every 7 days. During Part B of the double-blind phase (Weeks 5–24 of Panels 1–3 and Expansion Panel) and during the 48-week OL phase, the study drug should be administered every 7 days within a ±1-day window.

Subjects may receive the weekly dose at home, starting on Day 22. If the parent/caregiver has been trained by study site staff and is comfortable administering study drug to the subject, the parent/caregiver will receive an adequate supply of study drug in vial (either RO7239361 or placebo during the double-blind phase and RO7239361 in the OL and OLE phases) and sterile syringes for weekly administration at home to their child in between study visits. The first three weekly doses in the OL phase must be administered at the study site, *as well as the first two PFS doses in the OLE phase*.

In Panels 2 and 3, during the first four weeks of dosing (Days 1–29) the dose of RO7239361 should not be adjusted based on weight. Starting at Week 5, subjects whose weight exceeds or drops below the dosing weight tier to which they were assigned by >1 kg should be assigned to the new weight-based dose in the subject's assigned dose panel.

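### Section 3.1 keeps OLE subjects on their original panel's dose without ending that rule at the prefilled-syringe switch, and the weight-change sentence in Section 4.5 does not say how it works once a boy is on the syringe

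*Combined protocol and SAP*

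**What the plan says.** Section 3.1 deals with the OLE dose in three consecutive paragraphs.

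- The first has OLE subjects continuing on weekly doses "corresponding to the dose in their originally assigned panel for up to 228 weeks", or until commercial availability if that comes sooner. It sets no end at the PFS switch.
- The second makes the change of formulation follow approval of protocol Version 6 and renewed consent, and adds: "Subjects will continue to receive injections from a vial until the PFS becomes available at the site". It names no dose.
- The third says: "During the OLE phase, all subjects will switch from the vial formulation to PFS dosage formulation for weekly doses of study drug". It then gives the syringe dose as that of Panel 3, which means 35 mg from 15 to 45 kg, and "the 50-mg dose if the subject's body weight is >45 kg".

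The synopsis, under Study Design, agrees with the third paragraph: "all subjects will switch from the vial formulation to a prefilled syringe (PFS) dosage formulation corresponding to the same dose from Panel 3". Section 1.2 also presents the Panel 3 dose as the OLE dose after the change of presentation. The PFS is listed in two strengths only, 35 mg and 50 mg (synopsis Study Drug table, Tables 4-2 and 4-3).

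The weight-change rule in Section 4.5 is in a paragraph that opens by naming Panels 2 and 3. From Week 5, subjects "whose weight exceeds or drops below the dosing weight tier to which they were assigned by >1 kg" move to the new weight-based dose of the panel they were assigned to. The sentence has no end date and does not mention the PFS, although the paragraph before it does.

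**The concern.** This is the dosing instruction for the longest phase of a study in boys who were 5 to 10 years old at randomization. A site that follows the first OLE sentence in Section 3.1 to the letter would keep a Panel 1 or Panel 2 boy on his panel's dose throughout. A site that follows the third paragraph would move him to 35 or 50 mg.

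Section 4.5 adds a second gap. Section 4.5 anticipates weights of 15 to 70 kg, and weight is measured at the OLE visits, so movement across 45 kg should be expected. Once a boy is on PFS, the text does not say which panel's tier table governs him, or whether he changes tier at 45 kg exactly or only after passing it by more than 1 kg.

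There is a smaller consequence for the analysis. Sections 8.4.2, 8.4.5 and 8.4.6 tabulate function, myostatin and MRI data by dose, and the fifth interim analysis (Section 8.5) draws on OL and OLE data. Those tables are easier to define if the protocol gives one dose rule.

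**Working it through.** **Inputs.** Panel doses are from Tables 3.1-1 to 3.1-4: Panel 1, 4 mg with a single tier; Panel 2, 12.5 or 20 mg; Panel 3 and Expansion, 35 or 50 mg. The tier boundary is 45 kg wherever there are two tiers. PFS doses are from Section 3.1: 35 mg up to 45 kg, 50 mg above. Predicted weekly AUCs after the interim analysis are from Table 1.1-1 (µg·h/mL): 450, 1240 and 3620 for Panels 1, 2 and 3, and 5780 for the OLE on PFS. Planned sizes are from Section 8.1: about 8, 8, 8 and 16.

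**1. The plan's own OLE figure.** Panel 3 vial AUC × assumed formulation ratio = 3620 × 1.6 = 5792, against the stated 5780 (difference 12/5780 = 0.2%). The figure is reproduced, and it shows that the OLE exposure in Table 1.1-1 was worked out for the Panel 3 dose on PFS.

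**2. The two OLE dose statements in Section 3.1, in mg.**

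| Panel | Original-panel sentence (≤45 / >45 kg) | PFS sentence (≤45 / >45 kg) | Ratio |
|---|---|---|---|
| 1 | 4 / 4 | 35 / 50 | 35/4 = 8.75; 50/4 = 12.5 |
| 2 | 12.5 / 20 | 35 / 50 | 35/12.5 = 2.8; 50/20 = 2.5 |
| 3 and Expansion | 35 / 50 | 35 / 50 | 1; 1 |

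The statements differ in mg for 8 + 8 = 16 of 40 planned boys (40%) and agree for 8 + 16 = 24 of 40.

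**3. In exposure.** PFS against the panel's vial dose: 5780/450 = 12.8 and 5780/1240 = 4.7 for Panels 1 and 2. These ratios include the assumed 1.6-fold formulation effect. With the vial on both sides, the dose difference alone is 3620/450 = 8.0 and 3620/1240 = 2.9.

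**4. Section 4.5 applied literally to a boy on PFS.**

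- Panel 2: above 46 kg he goes to 20 mg, and below 44 kg to 12.5 mg. Neither is a PFS strength.
- Panel 3: he goes to 50 or 35 mg, both PFS strengths.
- Panel 1: the paragraph does not name this panel, which has one tier, so Section 4.5 gives no competing dose.
- Expansion: also not named. If it follows the Panel 3 table, the doses match.

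**5. The 1 kg margin, for a Panel 3 boy.**

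| Weight (kg) | Section 3.1, bare 45 kg | Section 4.5, previously 35 mg | Section 4.5, previously 50 mg |
|---|---|---|---|
| 43.5 | 35 | 35 | 35 |
| 44.5 | 35 | 35 | 50 |
| 45.5 | 50 | 35 | 50 |
| 46.5 | 50 | 50 | 50 |

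The rules part only within 1 kg of 45 kg, and only for a boy coming from the other tier. The difference there is 35 against 50 mg (50/35 = 1.43).

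**The case against.** The strongest reply is that Section 3.1 describes a sequence. The paragraph between the two dose statements ties the switch to Version 6 and renewed consent and keeps boys on vials until the PFS arrives. Section 1.2 speaks of the OLE dose after the switch, and the synopsis and Table 1.1-1 fit that. No 4, 12.5 or 20 mg PFS is provided. The 228 weeks can be read as a ceiling on treatment time. This largely stands: a reader might infer that the protocol prescribes two doses at the same moment, and the documents do not support that. What survives is that the original-panel sentence has no stated end and the bridging paragraph names no dose, so the sequence has to be inferred.

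Several other inferences also go too far.

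- That Section 4.5 fits no boy's PFS dose. For Panel 3, and for Expansion if it uses the same table, panel and PFS doses are equal in mg.
- That Section 4.5 conflicts for Panel 1. Its weight paragraph is confined to Panels 2 and 3.
- That there are two different weight boundaries. The boundary is 45 kg throughout. A tier table combined with a margin for changing tier is coherent; the gap is only that the text does not say whether the margin carries over to PFS.
- That the 12.8- and 4.7-fold AUC ratios measure the dose discrepancy. They mix dose with formulation.
- That OLE dose groups become unreliable. Containers are assigned through IWRS and home doses are recorded in diaries, so the dose given should be recoverable. The interim analyses are descriptive, without formal inference.

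**Conclusion.** The point holds in a limited form. Section 3.1 contains a current dosing sentence that, followed literally, keeps about 16 of 40 planned boys on a dose that the same section, the synopsis and Section 1.2 replace at the PFS switch. The difference is 8.75- to 12.5-fold in mg for Panel 1 and 2.5- to 2.8-fold for Panel 2. For the other 24 or so there is no difference in mg. In Section 4.5 the weight-change sentence points a Panel 2 boy on PFS to a dose that no syringe delivers, and the status of the 1 kg margin on PFS is open.

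This rests on two assumptions. The counts are planned panel sizes, not the numbers who entered the OLE. Section 4.5 is taken to apply in the OLE because its weight sentence has no end date; the protocol does not say either way. If it does not apply there, the text gives no margin or procedure for changing tier on PFS.

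No sample size, test or other statistical figure changes. Because this is a dosing instruction for children and costs little to put right, it deserves more than an editorial note.

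**What to change.** Reconcile the passages into one OLE dosing rule.

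- In Section 3.1, limit the original-panel sentence to the period the sponsor intends, and state which dose applies before and after the PFS switch.
- In Section 4.5, state which tier table governs a subject once he is on PFS, for every panel including Panel 1 and Expansion, and whether the margin of more than 1 kg applies to the PFS tiers.
- Check that the synopsis agrees with the result and that the IWRS dispensing logic implements it.

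Which dose and which weight rule apply is for the sponsor to decide. The cost is a few sentences of protocol text and one IWRS check. No new data or analyses are needed.
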